17.1.12 ADVERSE EVENTS BY SUBGROUPS

The subgroup factors of interest for AE summaries include: geographic region, sex, age group, number of prior hospitalizations for treatment of schizophrenia, duration of schizophrenia, and BMI category (see [Section 7.5](#)). AE by subgroup summaries are described in the individual sections above.

17.1.13 PSYCHIATRIC ADVERSE EVENTS LEADING TO DISCONTINUATION FROM STUDY (PAEDCs)

Additional information is collected for the non-serious psychiatric AEs that led to discontinuation from the study as well as for all serious psychiatric AEs within the study.

1. Could the psychiatric AE be accounted for by an exacerbation of the underlying mental illness? Describe how the symptoms or behaviors of the psychiatric AE are characteristic of or similar to those typically experienced by the patient and/or how they are atypical/different.
2. Describe any new psychosocial stressors that may have contributed to the event.
3. Describe any adverse reactions to other concomitant medications that may have accounted for / contributed to the event.
4. Describe any recreational drug use that may have accounted for / contributed to the event. Please provide results of any recent drug screens.
5. Describe any other medical conditions that could manifest with psychiatric symptoms that might have accounted for or contributed to the event.
6. Were there any new physical or neurological symptoms that emerged at the same time as worsening of psychiatric symptoms? Please provide any details of the medical review of body systems at the time of the event.

Document: CCI

Author: PPD

Version Number: 0.6

Version Date: 30JAN2023

Template No.: CS_TP_BS016 Revision 6

Reference: CS_WI_BS005

Effective Date: 02Dec2019

The above information is recorded in separate trackers and not part of the CRF. This information will be presented in separate data listings only.

17.2 LABORATORY EVALUATIONS

Results from the central laboratory to be reported for this study include Hematology, Chemistry (including lipid panel and thyroid panel), Urinalysis, Urine drug screening, Serology panel, Serum pregnancy (β -HcG) (in female subjects only), Urine pregnancy (in female subjects only), Follicle stimulating hormone (FSH) (in female subjects with suspected menopause). Due to the Russia-Ukraine geopolitical conflict, some patients from these regions will not be able to utilize the central laboratory and instead report results from local laboratories. These local laboratory results will be evaluated along the central laboratory results however not normalized against the central laboratory results. If, for a given visit, both local and central laboratory results are available, preference will be given to the central lab result.

Serum and urine pregnancy results in female subjects, FSH level in female subjects, serology panel, and any unexpected lab parameters not specified in protocol Section 21 (APPENDIX II. CLINICAL LABORATORY TESTS) will only be listed. Laboratory parameters prespecified in protocol Section 21 under the categories of "HEMATOLOGY", "BLOOD CHEMISTRIES" (plus HOMA-IR), "URINALYSIS", and "URINE DRUG SCREENING" will be summarized in tables as well as presented in listings.

Listing presentations will use both standard international (SI) Units and conventional units. Table summaries will also be provided using both SI units and conventional units.

Quantitative laboratory measurements reported as " $<X$ ", i.e. below the lower limit of quantification (BLQ), or " $>X$ ", i.e. above the upper limit of quantification (ULQ), will be converted to X for the purpose of quantitative summaries, but they will be presented as recorded, i.e. as " $<X$ " or " $>X$ " in the listings.

The following summaries will be provided:

- By-visit summary of observed values and change from Baseline values for quantitative measurements in hematology, chemistry, and urinalysis. Serum prolactin results will be summarized overall and separately by sex. Glucose, insulin, HOMA-IR, and lipid panel results (total cholesterol, LDL cholesterol, HDL cholesterol and triglycerides) will be summarized by fasting status: fasting only and overall (fasting, non-fasting, or fasting status unknown combined). Change from Baseline for glucose, insulin, HOMA-IR, and lipid panel results will only be calculated if post-Baseline fasting

Document: CCI

Author: PPD

Version Number: 0.6

Version Date: 30JAN2023

Template No.: CS_TP_BS016 Revision 6

Reference: CS_WI_BS005

Effective Date: 02Dec2019

status is matching Baseline fasting status.

- By-visit summary of the number and percentage of subjects in each outcome category for qualitative measurements in urinalysis (as applicable) and for urine drug screening results. Urine drug screening results will be reported as “Positive”/ “Negative”.
- Shift in laboratory results (chemistry, hematology, urinalysis) from Baseline to Week 1/Visit 3, Week 4/Visit 5, Week 12/Visit 7, Week 24/Visit 10, Week 36/Visit 13, Week 52/Visit 17, and LOCF Endpoint according to the reference range criteria. The existing reference range indicators provided by the central laboratory will be mapped as needed to categories of “Normal” (within the reference range) / “Abnormal” (outside the reference range) for urinalysis non-pH results, and to categories of “Low” (below the reference range) / “Normal” (within the reference range) / “High” (above the reference range) for chemistry and hematology results as well as urinalysis pH results.
- Number and percentage of subjects with at least one potentially clinically significant (PCS) laboratory value (see [APPENDIX 8](#)) post-Baseline. The period of evaluation includes both the double-blind treatment period and the follow-up period up to and including 9 days after the last dose of study drug, including unscheduled visits. Subjects will be counted in a particular PCS category if they met that PCS criteria at least once during the period of evaluation, regardless of their Baseline value.
- The change from Baseline values at Week 52/Visit 17 and LOCF Endpoint for selected laboratory parameters will be evaluated using a nonparametric rank ANCOVA analysis to compare SEP-363856 50 to 100 mg/day and Quetiapine XR 400 to 800 mg/day treatment groups. Baseline values and change from Baseline values will be ranked. A linear regression analysis will be performed on the change from Baseline value ranks with the Baseline value ranks as the independent variable, to produce regression residuals. Using the values of the residuals as scores, the Cochran-Mantel-Haenszel row mean scores test will be used to compare between the SEP-363856 and Quetiapine XR treatment groups. This analysis will be conducted for prolactin (overall and by sex), glucose (overall and fasting), insulin (overall and fasting), HOMA-IR (overall and fasting), lipid panel (overall and fasting), and HbA1c.

In order to assess the potential cardiometabolic effect of SEP-363856, select laboratory parameters will be summarized based on the subgroup of subjects who are identified to be metabolically impaired at Baseline (see [Section 17.2.3](#)) and on the subgroup of subjects who are non- metabolically impaired at Baseline. The following summaries will be provided on this subset of subjects:

Document: **CCI**

Author: **PPD**

Version Number: 0.6

Version Date: 30JAN2023

Template No.: CS_TP_BS016 Revision 6

Reference: CS_WI_BS005

Effective Date: 02Dec2019

- By-visit summary of observed values and change from Baseline values for LDL, HDL, total cholesterol, triglycerides, glucose, and HbA1c. LDL, HDL, total cholesterol, triglycerides, and glucose results will be summarized by fasting status: fasting only and overall (fasting, non-fasting, or fasting status unknown combined). Change from Baseline for LDL, HDL, triglycerides, and glucose results will only be calculated if post-Baseline fasting status is matching Baseline fasting status.

All laboratory data will be provided in data listings, with the values outside the reference ranges flagged. In addition, separate listings will be provided to present the laboratory data that met the PCS criteria.

A boxplot will be created to present Baseline, Week 1/Visit 3, Week 4/Visit 5, Week 12/Visit 7, Week 24/Visit 10, Week 36/Visit 13, and Week 52/Visit 17 values by treatment group for lipid parameters (total cholesterol, LDL, HDL, and triglycerides) and glucose by fasting status: fasting only and overall (fasting, non-fasting, or fasting status unknown combined). In addition, a boxplot will be created to present Baseline, Week 1/Visit 3, Week 4/Visit 5, Week 12/Visit 7, Week 24/Visit 10, Week 36/Visit 13, and Week 52/Visit 17 prolactin values by treatment group by sex: Overall, males, females. Lastly, the values of HbA1c will be presented by visit and treatment group in a boxplot as well. Results of LDL, HDL, triglycerides, glucose, and HbA1c will be plotted for all subjects, for the subset of subjects who are metabolically impaired at Baseline, and for the subset of subjects who are non-metabolically impaired at baseline. Each of these boxplots will be repeated to present the change from Baseline values.

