3.2. METHOD OF ASSIGNING SUBJECTS TO TREATMENT GROUPS

The randomization schedule is generated by a non-study biostatistician.

The randomization is stratified by country and the randomization schedule is based on permuted blocks.

Once a subject is deemed eligible to be randomized at Day 1, an interactive web response system (IWRS) will perform treatment assignment. Subjects will be randomized to one of the following treatment groups in a 2:1 ratio:

- Flexibly dosed SEP-363856 (50, 75, or 100 mg/day) for 52 weeks
- Flexibly dosed Quetiapine XR (400, 600, or 800 mg/day) for 52 weeks

Once a randomization number has been assigned, it cannot be reused.

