- BARS: total score and individual item scores. For a given subject, the Baseline values for all BARS summary and individual item scores should come from the same assessment and it should be the last assessment prior to first dose where BARS total score is available. In the rare event where no BARS total score is available before first dose due to partially completed assessments, the assessment prior to first dose with most BARS item scores available should be taken as the Baseline assessment for all raw and derived scores as applicable.
- AIMS: total score and individual item scores. For a given subject, the Baseline values for all AIMS summary and individual item scores should come from the same assessment and it should be the last assessment prior to first dose where AIMS total score is available. In the rare event where no AIMS total score is available before first dose due to partially completed assessments, the assessment prior to first dose with most AIMS item scores available should be taken as the Baseline assessment for all raw and derived scores as applicable.
- Clinical laboratory parameters (blood chemistry, hematology, urinalysis, HOMA-IR). For a given subject, the Baseline values for the clinical laboratory parameters do not have to all come from the same assessment; the only exception is: the Baseline flag for the counts of leukocytes and its differential should be applied to records from the same assessment and it should be the last assessment prior to first dose where counts of leukocytes and its differential are reported. Baseline flag does not need to be derived for RBC morphology findings, WBC morphology findings, and urinalysis microscopic examination findings (excluding urine erythrocytes and leukocytes). Where results are available for both central laboratory and local laboratory for a given assessment, the central laboratory result will be considered baseline.
- Urine drug screening: For a given subject, the Baseline values for all urine drug screening parameters should come from the same assessment and it should be the last assessment prior to first dose where a urine drug screening test was administered.

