Author: PPD

Version Number: 0.6

Version Date: 30JAN2023

Template No.: CS_TP_BS016 Revision 6

Reference: CS_WI_BS005

Effective Date: 02Dec2019

where counts of leukocytes and its differential are reported. LOCF endpoint does not need to be derived for RBC morphology findings, WBC morphology findings, and urinalysis microscopic examination findings (excluding urine erythrocytes and leukocytes). Where results are available for both central laboratory and local laboratory for a given assessment, the central laboratory result will be considered LOCF endpoint.

- Urine drug screening (adolescent subjects only): For a given subject, the LOCF values for all urine drug screening parameters should come from the same assessment and it should be the last post-Baseline assessment up to and including Visit 17 (EOT/ET) measurement and within 9 days post the last dose where a urine drug screening test was administered.
- Vital sign parameters (supine and standing SBP, supine and standing DBP, supine and standing pulse rate, respiratory rate, oral temperature), height, weight, BMI, and waist circumference. For a given subject, the LOCF values for all vital sign parameters, height, weight, BMI, and waist circumference do not have to come from the same assessment; the only exceptions are: (1) the LOCF flag for weight and BMI should be applied to records from the same assessment and it should be the last post-Baseline assessment up to and including Visit 17 (EOT/ET) measurement and within 9 days post the last dose where weight is available, (2) the LOCF flag for supine systolic and diastolic blood pressure, standing systolic and diastolic blood pressure, and the derived corresponding orthostatic endpoints (i.e. standing SBP – supine SBP; standing DBP – supine DBP) should be applied to records from the same assessment and it should be the last post-Baseline assessment up to and including Visit 17 (EOT/ET) measurement and within 9 days post the last dose where all four BP measures are available, and (3) the LOCF flag for supine and standing pulse rate and the derived corresponding orthostatic endpoint (i.e. standing pulse rate – supine pulse rate) should be applied to records from the same assessment and it should be the last post-Baseline assessment up to and including Visit 17 (EOT/ET) measurement and within 9 days post the last dose where both pulse rate measures are available.

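### Local and central laboratory results are pooled with no normalisation and no laboratory matching, so any assay difference enters the metabolic and prolactin changes from Baseline

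*SAP*

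**What the plan says.** SAP section 17.2 explains that, because of the conflict, "some patients from these regions will not be able to utilize the central laboratory and instead report results from local laboratories". It continues: "These local laboratory results will be evaluated along the central laboratory results however not normalized against the central laboratory results".

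The plan has one rule for choosing between sources. In section 6.2: "Where results are available for both central laboratory and local laboratory for a given assessment, the central laboratory result will be considered baseline". Section 6.3 applies the same preference, so that "the central laboratory result will be considered LOCF endpoint", and sections 17.2 and 17.2.1 repeat it. The rule acts only when both results exist for the same assessment or visit.

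The only pairing condition on change from Baseline concerns fasting. For glucose, insulin, HOMA-IR and the lipid panel, change is calculated only when the post-Baseline "status is matching Baseline fasting status". The metabolic-impairment subgroups carry a similar condition: "Change from Baseline for LDL, HDL, triglycerides, and glucose results will only be calculated if post-Baseline fasting status is matching Baseline fasting status". Prolactin and HbA1c have no pairing condition.

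For the rank ANCOVA at Week 52 and LOCF: "A linear regression analysis will be performed on the change from Baseline value ranks with the Baseline value ranks as the independent variable". The residuals then go into a Cochran-Mantel-Haenszel (CMH) row mean scores test, for which no strata are named. Section 3.2 says of the design: "The randomization is stratified by country and the randomization schedule is based on permuted blocks".

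**The concern.** Subtracting a central Baseline from a local later value gives the subject's change plus the difference between the two laboratories. The plan will not difference values from unlike fasting states, but it does difference values from unlike laboratories. Protocol section 11.5.2 gives consistency as the reason for using a central laboratory, and that protection is lost for these subjects.

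The comparison with quetiapine XR on prolactin, HbA1c, lipids and glucose is a named safety objective (Protocol 5.2, SAP 2.1.2). Two things are at stake.

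- **Within-arm change.** Randomisation cannot remove a laboratory shift from the by-visit change summaries, the metabolic-impairment subgroups or the change boxplots. HOMA-IR multiplies two assays, so it carries both differences.
- **Between-arm test.** The shift adds variance to the rank ANCOVA. The SAP's MMRM and parametric ANCOVA models (16.1.1.1, 16.1.1.3) include country; the rank ANCOVA does not, although local-laboratory use is tied to particular countries.

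**Working it through.** **1. Can a mismatched pair enter the analysis?** Take a subject whose Baseline went to the central laboratory and whose only Week 52 result is local. Section 6.2 gives a central Baseline. The preference rules do not apply at Week 52, because no central result exists. If fasting status matches, or the parameter is prolactin or HbA1c, the change is calculated and ranked. I found no same-laboratory restriction and no sensitivity analysis by source.

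**2. The plan's own figures.** No power, effect size or assay difference is stated for any laboratory comparison. Protocol 15.1 gives 300 subjects at 2:1, so 200 and 100, with about 80 SEP-363856 completers: 80/200 = 40%. The same completion on quetiapine XR, which is an assumption, gives 100 × 0.40 = 40. An 80/40 split therefore approximates Week 52. LOCF would have more subjects.

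**3. Within-arm mean change.** With a share p of mismatched pairs and a laboratory difference d, the mean change moves by p × d. For p = 25% (assumed):
- d = 0.5 SD: 0.25 × 0.5 = 0.125 SD
- d = 1 SD: 0.25 × 1 = 0.25 SD

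**4. Power.** The procedure in 17.2 was simulated: rank Baseline and change, regress change ranks on Baseline ranks, then test the residuals. With two arms and one stratum the statistic is Z = (sum of residuals in arm 1 − n1 × overall mean) / √(n1·n0·s²/n), compared with ±1.96. Assumptions: true difference 0.45 SD, Baseline correlation 0.5, 25% local in both arms, one common shift, 3,000 runs.

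| Subjects | Shift | Planned test | Stratified central/local |
|---|---|---|---|
| 120/60 | none | 88% | 88% |
| 120/60 | 0.5 SD | 86% | 88% |
| 120/60 | 1 SD | 80% | 88% |
| 80/40 | none | 73% | not shown |
| 80/40 | 1 SD | 64% | 71% |

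The losses are 88 − 86 = 2 points, 88 − 80 = 8 points and 73 − 64 = 9 points. Simulation error is under 1 point per cell.

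**5. Type I error.** Runs at 80/40 with correlation 0.6:
- Equal local share by arm (10% to 50%), shift 0 to 1 SD: 4.7% to 5.6%.
- Local share 40% in one arm and 20% in the other, either way round: 9% to 10% at a 0.5 SD shift and 19% to 21% at 1 SD. Stratifying by source brings this back to about 5%.

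**6. What the remedies recover.** The recovery in step 4 depends on one shift shared by all local laboratories. With eight local laboratories whose shifts vary at random (120/60, 25% local), a central/local stratum barely helps: 83.1% pooled against 82.9% stratified when the shifts have SD 0.5, and 77.0% against 78.8% when they have SD 1.

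Restricting to central-central pairs removes the shift but costs subjects. At 80/40 with a true difference of 0.5 SD, the full set with no shift has about 87% power. The restricted set has 81% to 84% if 10% of values are local, 72% to 73% if 30% are, and 56% to 57% if 50% are.

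**The case against.** The best defence is that the treatment comparison remains valid. Randomisation is stratified by country, so local use should be similar in the two arms, and step 5 shows type I error near 5% when it is. A reader might infer that the p-values against quetiapine XR are biased. That needs local use to differ by arm among those analysed, for example through unequal dropout before the switch, and the documents do not establish this.

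The size can also be challenged. The documents speak only of some patients, with no count, switch date or assay difference. At a 0.5 SD common shift the power loss is trivial. Nor do the documents show that every affected subject has a central Baseline: a local Baseline is possible, and an additive shift cancels within one local laboratory. In one set of runs (120/60, 25% local, 1 SD shift), letting half of the local subjects have such pairs raised pooled power from 77% to 80%.

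The stakes are limited. These are other safety analyses with nominal p-values (SAP 7.4), and sample size was not set on power. There is partial handling too: central results are preferred where both exist, out-of-range values are flagged in listings, and the lack of normalisation is disclosed.

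All of this stands as a limit on size. None of it removes the shift from the within-arm changes, and none of it lets a reader of the planned tables separate drug effect from laboratory difference.

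**Conclusion.** The gap is in the text: the plan matches fasting status but never laboratory, and the rank ANCOVA has no stratum that could absorb the difference. The well-supported harms are contaminated within-arm changes and some lost power. Under the assumed 25% local share and one common shift, the mean change moves by 0.125 to 0.25 SD, and power falls by about 2 points at 0.5 SD and 8 to 9 points at 1 SD. These figures are illustrative, because the true share and shift are not in the documents. A false-positive problem between arms is conditional on unequal local use and should not be claimed from the plan. The adverse-event primary endpoint, weight and BMI are not affected. The point merits a change because the remedy is cheap, not because a large effect has been shown.

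**What to change.** 1. In SAP 17.2, stratify the rank ANCOVA and CMH test by country. This is the randomisation stratum and is fixed before treatment. It absorbs only the between-country part of the shift.
2. Add a sensitivity version of the rank ANCOVA, the by-visit change tables and the boxplots, limited to same-laboratory Baseline and post-Baseline pairs (central-central, or the same local laboratory).
3. Add a rank ANCOVA version stratified by source pair (same or different laboratory), collapsing sparse or single-arm strata. Avoid crossing source with country: with four countries, about 120 completers and prolactin split by sex, cells may be empty. Keep this as a sensitivity version, because endpoint source is determined after randomisation.
4. Tabulate local results by arm and visit, so that readers can see the share and whether it is balanced.

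The cost is SAP wording and a few extra tables. The central-preference rule already requires central and local results to be told apart; the same-laboratory version also needs each local laboratory identified. That version has fewer subjects, and stratifying by source pair recovers little power if the local laboratories differ from one another.

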11.7.1. Screening: Visit 1 (Day -21 to -1)

After a subject provides consent, a unique subject number will be assigned at screening by the IWRS, consisting of a 3-digit protocol number, 3-digit site number, and a unique 3-digit subject identifier (eg, the second screened subject from site #005 will be 304005002). Subjects will be numbered consecutively. No subject numbers are to be reused once assigned. This number will track a subject throughout their participation in the study.

Subjects will be evaluated at the Screening Visit to determine their eligibility for the study. The subject's eligibility assessment will be reviewed by the contract research organization's (CRO) oversight quality team along with the sponsor based on protocol specified inclusion and exclusion criteria. In the event the CRO/sponsor and site do not agree on a subject's eligibility then the subject will not be enrolled.

Subjects found to be ineligible during Visit 1 will not be required to complete all the Visit 1 assessments and will not be followed upon leaving the study.

Subjects who screen fail may be re-screened once, if judged appropriate by the Investigator, after discussion with the Medical Monitor. Re-screened subjects will be re-consented, assigned a new subject number, and all Visit 1 procedures will be repeated.

The Screening Period may be extended for up to 7 days after approval from the Medical Monitor.

The following procedures will be conducted during this visit:

- Obtain signed informed consent and privacy authorization (if applicable or required by local law) from the subject before conducting any other visit procedures, including informed consent for duplicate subject check (where allowed by local/regional regulations)
- CCI
- Review inclusion and exclusion criteria
- Collect prior and concomitant medications
- Obtain demographic information
- Collect adverse events (Note: events occurring prior to first dose of study drug will be identified programmatically as pretreatment events.)
- Collect medical history
- Collect psychiatric history
- SCID-CT
- Physical and neurological examination
- Height and weight; clinical site staff to calculate and record BMI
- Vital sign measurements
- Standard 12-lead ECG
- Fasted blood samples for clinical laboratory evaluation (hematology and serum chemistry)

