6.2. BASELINE

Unless otherwise specified, Baseline is defined as the last non-missing measurement taken prior to the reference start date (including unscheduled assessments).

Whenever available, the time information should be accounted for in the derivation of Baseline values. In the case where time is not available and the date of the last non-missing measurement and the date of the first dose of study medication coincide, that measurement will be considered the Baseline.

Baseline will be derived for the following outcome measures:

Document: CCI

Author: PPD

Version Number: 0.6

Version Date: 30JAN2023

Template No.: CS_TP_BS016 Revision 6

Reference: CS_WI_BS005

Effective Date: 02Dec2019

- PANSS: total score, subscale scores, Marder factor scores, UPSM factor scores and total factor score, and individual item scores. For a given subject, the Baseline values for all PANSS summary and individual item scores should come from the same assessment (i.e. have the same visit number and assessment start date/time) and it should be the last assessment prior to first dose where PANSS total score is available (i.e. not set to missing). In the rare event where no PANSS total score is available before first dose due to partially completed assessments, the assessment prior to first dose with the most PANSS item scores available should be taken as the Baseline assessment for all raw and derived scores as applicable.
- CGI-S score.
- BNSS: total score, subscale scores, and individual item scores. For a given subject, the Baseline values for all BNSS summary and individual item scores should come from the same assessment and it should be the last assessment prior to first dose where BNSS total score is available. In the rare event where no BNSS total score is available before first dose due to partially completed assessments, the assessment prior to first dose with most BNSS item scores available should be taken as the Baseline assessment for all raw and derived scores as applicable.

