6.3. DERIVED TIMEPOINTS

The last non-missing post-Baseline (i.e., post-first dose) measurement collected up to and including the Visit 17 (EOT/ET) measurement and within 9 days post the last dose will be carried forward and defined as the last observation carried forward (LOCF) endpoint. Both scheduled and unscheduled assessments as well as the early termination assessments that are collected during this period will contribute to the derivation of the LOCF endpoint. However, scheduled and unscheduled measurements taken after the Visit 17 (EOT/ET) measurement or beyond 9 days post the last dose will not be used in the derivation.

Document: CCI

Author: PPD

Version Number: 0.6

Version Date: 30JAN2023

Template No.: CS_TP_BS016 Revision 6

Reference: CS_WI_BS005

Effective Date: 02Dec2019

The LOCF endpoint will be derived for the following outcome measures:

- PANSS: total score, subscale scores, Marder factor scores, UPSM factor scores and total factor score, individual item scores, and derived binary variables for PANSS response. For a given subject, the LOCF values for all PANSS summary and individual item scores and derived binary variables should come from the same assessment and it should be the last post-Baseline assessment up to and including Visit 17 (EOT/ET) measurement and within 9 days post the last dose where PANSS total score is available. In the rare event where no PANSS total score is available after first dose due to partially completed assessments, the last post-Baseline assessment up to and including Visit 17 (EOT/ET) measurement and within 9 days post the last dose should be taken as the LOCF assessment for all raw and derived scores as applicable.
- CGI-S score.
- BNSS: total score, subscale scores, and individual item scores. For a given subject, the LOCF values for all BNSS summary and individual item scores should come from the same assessment and it should be the last post-Baseline assessment up to and including Visit 17 (EOT/ET) measurement and within 9 days post the last dose where BNSS total score is available. In the rare event where no BNSS total score is available after first dose due to partially completed assessments, the last post-Baseline assessment up to and including Visit 17 (EOT/ET) measurement and within 9 days post the last dose should be taken as the LOCF assessment for all raw and derived scores as applicable.

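### Baseline and LOCF values for glucose, insulin, HOMA-IR and lipids are chosen without regard to fasting status, but change is calculated only when the statuses match, so usable fasted pairs can be discarded

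*SAP*

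**What the plan says.** SAP 6.2 sets the general rule: "Baseline is defined as the last non-missing measurement taken prior to the reference start date", unscheduled samples included. For laboratory parameters it adds that "the Baseline values for the clinical laboratory parameters do not have to all come from the same assessment", with an exception for the leukocyte differential and a preference for central over local results. Fasting is not mentioned.

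SAP 6.3 defines LOCF as "The last non-missing post-Baseline (i.e., post-first dose) measurement collected up to and including the Visit 17 (EOT/ET) measurement", subject to a limit of 9 days after the last dose. Samples from scheduled, unscheduled and early termination visits all count. The laboratory bullet again has no fasting condition.

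SAP 17.2 summarises glucose, insulin, HOMA-IR and lipids twice: fasting only, and overall (fasting, non-fasting and unknown status combined). In the by-visit bullet it states "Change from Baseline for glucose, insulin, HOMA-IR, and lipid panel results will only be calculated if post-Baseline fasting" status is the same as at Baseline. The rank ANCOVA compares the arms on change at Week 52 and at LOCF for prolactin, glucose (overall and fasting), "insulin (overall and fasting), HOMA-IR (overall and fasting), lipid panel (overall and fasting), and HbA1c".

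The protocol's schedule of assessments requires subjects to be fasted for these tests. Section 11.7.1 lists "Fasted blood samples for clinical laboratory evaluation (hematology and serum chemistry") at Screening, and the later visit lists ask for fasted blood at Visit 2, at Weeks 1, 4, 12, 24 and 36, and at the combined Week 52/EOT/ET visit.

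**The concern.** Fasting status plays no part in choosing the two samples but then decides whether the pair may be used. There is no step back to an earlier fasted sample, so a subject with a valid fasted pair can end up with no change value. Two patterns produce this:

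- **Baseline side.** Fasted at Screening, not fasted at Visit 2. Visit 2 becomes Baseline, and every later fasted sample fails the match.
- **LOCF side.** Fasted at Baseline and at intermediate visits, not fasted at the last sample. The last sample becomes LOCF and fails the match.

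Both patterns also remove the subject from the overall change at those time points, so that analysis does not combine all statuses as its label suggests. At stake is the stated safety objective of comparing effects on lipids and glucose with quetiapine XR. Any loss on these patterns is avoidable, because the fasted samples have already been collected.

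**Working it through.** **The rules side by side**

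| Step | SAP section | Uses fasting status? |
|---|---|---|
| Choose Baseline | 6.2 | No |
| Choose LOCF | 6.3 | No |
| Calculate change | 17.2, by-visit bullet | Yes, statuses must match |
| Rank ANCOVA on change | 17.2, rank ANCOVA bullet | Not restated; analyses the same change variable |

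The SAP does make sample choice depend on usability elsewhere. Blood pressure Baseline and LOCF, for example, come from the last assessment with all four measures present.

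**Figures in the plan.** None bears directly on this point: the documents give no fasted or non-fasted rate. The sample size section expects about 80 SEP-363856 completers. With 300 randomised 2:1, that arm has 300 × 2/3 = 200 subjects, so 80/200 = 40% complete and 60% do not. This shows that LOCF would often rest on a sample taken before Week 52. It says nothing about whether that sample was fasted.

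**Illustration of size.** Assume each sample is non-fasted or of unknown status (treated as one category) with probability q, independently. Allow two pre-dose samples (Screening and Visit 2) and k = 3 post-dose samples.

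- SAP rule, fasting analysis: (1 − q)²
- SAP rule, overall change: (1 − q)² + q²
- Mismatched pairs: 2q(1 − q)
- Last fasted sample at each end, LOCF: (1 − q²)(1 − q³)
- Last fasted Baseline, Week 52: (1 − q²)(1 − q). The Week 52 sample itself has no substitute.

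| q (assumed) | Fasting, SAP rule | Overall, SAP rule | Mismatched | Fasting LOCF, fasting-aware | Fasting Week 52, fasting-aware |
|---|---|---|---|---|---|
| 2% | 96.0% | 96.1% | 3.9% | 100.0% | 98.0% |
| 5% | 90.3% | 90.5% | 9.5% | 99.7% | 94.8% |
| 10% | 81.0% | 82.0% | 18.0% | 98.9% | 89.1% |
| 20% | 64.0% | 68.0% | 32.0% | 95.2% | 76.8% |

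Under this model the SAP-rule fasting column applies to Week 52 and LOCF alike. As counts, if all 300 subjects had an LOCF pair and q = 10%, the fasting analysis would keep 300 × 0.81 = 243 subjects, against 300 × 0.989 ≈ 297. The LOCF gain depends modestly on k: at q = 20% it reaches 92.2% with k = 2 and 96.0% with k = 6.

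If the same subjects tend to be non-fasted repeatedly, the mismatched share is smaller than shown and fewer subjects are recoverable.

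**The case against.** The strongest reply is that no loss has been shown. The protocol requires fasting and repeats it at every scheduled laboratory visit; with full compliance nothing is lost, and at 2% non-fasted the current rule keeps 96%. That stands, and the size has to be left open. It does not remove the defect, because SAP 17.2 itself provides for non-fasting and unknown-status samples.

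Second, the matching sentence sits in the by-visit bullet and is not repeated for the rank ANCOVA. That is correct. Applying it there is an inference, though a direct one: the ANCOVA ranks change from Baseline for the same parameters, and no other definition of that change is given.

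Third, a fasting-only analysis could be programmed with a fasting-specific Baseline, since SAP 17.2.3 refers to fasting values at Baseline. No rule says how those are chosen, and SAP 6.2 governs unless something else is specified.

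Fourth, substitutes have a price. A Screening value may precede washout of a prior antipsychotic, and a last fasted value may be much older than the last sample. Both points stand and belong in the reporting. SAP 6.2 already accepts a Screening value when Visit 2 is missing.

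A reader might also infer that early-termination samples are the ones most often non-fasted, so that discontinuers are lost preferentially and the comparison is biased. The documents do not support this: protocol 11.7.17 asks for a fasted sample at ET, no ET fasting rate is given, and nothing indicates a difference between arms. Nor do they support calling an overall HOMA-IR analysis invalid: SAP 17.2.1 gives the formula without a fasting condition, and a fasting-only version is already planned.

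**Conclusion.** The point holds as a defect in how the rules combine. Read literally, SAP 6.2, 6.3 and 17.2 discard subjects who have a usable fasted pair, from the by-visit change summaries and, by inference, from the rank ANCOVA.

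It is limited to glucose, insulin, HOMA-IR and lipids. It would be too much to say that these subjects leave the metabolic comparison altogether: HbA1c, prolactin, weight and BMI carry no fasting rule, and observed values, potentially clinically significant counts and boxplots of observed values still include them.

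The size is unknown. All percentages in the table rest on an assumed, independent non-fasted rate. The benefit of a change is larger at LOCF than at Week 52, the only time point that the protocol synopsis names for this analysis. Unequal or informative loss at ET is possible but not shown. The analyses affected are other-safety comparisons with nominal p-values. The change is worth making because it is cheap, not because a material bias has been demonstrated.

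**What to change.** 1. For the fasting analyses of glucose, insulin, HOMA-IR and lipids, define Baseline as the last fasted pre-dose value, Screening included, and LOCF as the last fasted post-Baseline value in the existing window. Calculate change from these for both the by-visit summaries and the rank ANCOVA.
2. Keep the matching rule for the overall change; without it, fasted values would be subtracted from non-fasted ones. Label that analysis as matched-status pairs only, state that the rule also governs its rank ANCOVA, and say how unknown status is matched.
3. Use the same fasting Baseline in SAP 17.2.3. Also settle whether total cholesterol falls under matching in the metabolic-impairment subgroups, where the SAP 17.2 sentence omits it although the main rule covers the whole lipid panel.
4. Report by arm how many subjects use a Screening value as fasting Baseline and how many use a fasting LOCF value from before their last sample.

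The cost is SAP wording and one additional Baseline and LOCF flag per parameter; no new samples are needed. The downside is that some fasting Baselines may precede washout and some fasting LOCF values will reflect shorter exposure. The counts in item 4 let a reader judge how much that matters.
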